05/18/2021

**Periapical Healing following Endodontic Microsurgery with
Collagen Based Bone Filling Material: A Randomized Controlled
Clinical Trial**

NCT04514991

Protocol:

Subjects are recruited for the study from the patient pool of the Department of Endodontics, School of Dental Medicine, University of Pennsylvania, who are planned for routine treatment of root end surgery. Patients who present to the post-doctoral resident clinic and meet the inclusion criteria are asked to participate in the study. The study includes lesions classes B and C, as described by Kim and Kratchman, J Endod 2006. Teeth designated as Class B present with a small periapical lesion, normal periodontal probing depth, and no mobility. Patients with such teeth often have clinical symptoms, and such cases are ideal for microsurgery. Teeth with Class C designation have a sizeable periapical lesion with a coronal extension of the lesion but without periodontal pocket or mobility.

Randomization is done for single-rooted teeth assigned as either control or test group receiving Foundation bone augmentation material (Morita, Tokyo, Japan). Osteotomy sites in the control group will be closed without placing bone filling material or membrane. For multirooted teeth with noncommunicating osteotomy sites, one osteotomy site is designated as control, and the other site is filled with Foundation bone filling material. Treatments for all patients in control and experimental groups follow the standard of care practices, routinely performed based on surgical guidelines as outlined in Kim and Kratchman, J Endod 2006.

Patients are thoroughly informed about the nature of the surgical procedure and are briefed about potential risks and alternatives by the resident performing the surgery. The performing resident obtains a written consent form for the surgical procedure. The co-investigator briefs the patient about the nature of the study and obtains a separate written consent form for participation in this study. The resident performing the surgery evaluates and treatment plans the case through a clinical and radiographic examination of the involved teeth. Radiographs of the involved tooth and limited-volume cone-beam computed tomography (CBCT) of the defect area are obtained during the consultation as routine protocol for root-end surgery requires. The lesion is assessed for size, location, and proximity to other anatomical structures such as infra-alveolar or mental nerves, sinus cavity, or adjacent roots. On the day of surgery, the resident conducts and completes the surgery as standard protocol requires, including medical history update, local anesthesia administration, flap elevation, and obtaining access to the root tips and the periapical lesion through the removal of bone. Using the surgical microscope, the lesion is examined, 3 mm of the root tip is resected, and the root is stained and inspected for root fracture, missed canals, or isthmus as routinely done during root end surgery. If the fracture line on the root surface is detected, the subject will be excluded from the study. The fractured tooth may be extracted, or the patient will be referred for tooth extraction at a different time after repositioning the flap and suturing. In all other cases, routine surgery will continue with 3 mm of preparation for root-end cavity using ultrasonic tips and filled with bioceramic putty (EndoSequence BC-RRM Fast-Set Putty; Brasseler, Savannah, GA, USA). A post-operative periapical radiograph is taken to verify the position of retrograde filling. The osteotomy site is

then curetted to induce bleeding inside of the surgical site. The co-investigator conducts the randomization of the case. Using a publicly available randomization application, Randomizer for Clinical Trials, single-rooted teeth will be assigned as either control or test group receiving Foundation. For multirooted teeth, the mesial root will be randomized, and the distal root will receive the other treatment. For teeth assigned to receive Foundation, a sterile instrument is used to remove the material from the plastic container and placed in the osteotomy site. In the control group, the osteotomy site is left unfilled, flap repositioned, and sutures placed. Patients are given post-operative instructions and scheduled for follow-up and suture removal 3-5 days after the surgery. PDM chart number, which is patient-specific are accessed only by the provider, PI and co-investigator (for follow-up procedures). Tooth number, gender, age, and list of potential clinical symptoms, the date of surgery (necessary only for a description of the study population for publication) are collected and forwarded to the principal investigator (PI). Several prognostic factors are evaluated such as subject's sex, age, tooth involved, diagnosis, clinical symptoms, lesion classification, treatment rendered before EMS (primary non-surgical root canal treatment, nonsurgical retreatment, previous history of apical surgery). Preoperative CBCT scan is evaluated for the following possible prognostic factors:

- 1) Presence of cortical plate fenestration. This information was verified clinically during surgery.
- 2) Thickness of the buccal bone: measured 3 mm coronally from the apex on the B-L view.
- 3) Lesion size: height, depth and width of the lesion were measured. The value of the largest dimension was recorded as the lesion size.
- 4) Root angulation: measured between the long axis of the root and a line tangent to the cortical plate at the resection area.

Follow up visits are scheduled, as routinely practiced, every six months following the procedure. At six-month follow-up, periapical radiographs are taken. At 12-month follow-up, digital periapical radiographs and CBCT are obtained. In all follow-up visits, clinical signs and symptoms are evaluated. Molven's success criteria is applied to evaluate healing with periapical radiographs. For outcome assessment, cases will be designated as complete healing, incomplete healing, uncertain or unsatisfactory healing. Healing assessment on CBCT will be classified using modified PENN criteria as complete healing, limited, uncertain, or unsatisfactory healing. In complete healing, there is complete bone repair covering the resected root area, and the periodontal space is reformed with normal width or less than twice the width of the non-involved parts of the root. On the other hand, limited healing is characterized by complete healing in the vicinity of the resected root, but there is a discontinuity of the cortical plate with areas of low density. Low-density areas might also be present asymmetrically around the apex in limited healing or in the former access osteotomy. When the location of the low-density area is symmetrical around the apex or when the thickness is larger than twice the width of periodontal space, healing is classified as uncertain. Lastly, in unsatisfactory healing, the area of low density appears enlarged or unchanged. The co-investigator will be available during the follow-up appointments. All radiographs taken will be coded by case number (derived from the randomization table) and a suffix designating the time the radiograph was taken. Radiographs will be taken at three-time intervals PRE (preoperative, periapical, and CBCT), POP (immediate post-operative, periapical), FU1 (6-month follow-up, periapical), and FU2 (12-month follow-up,

periapical and CBCT). Hence, every single radiograph can be traced accordingly by case number and interval. For example, 002-FU2 equals 12- month follow-up of case number 2. The co-investigator will not evaluate the radiographs herself, since she will be the only one able to reconnect case radiographs with the treatment used. Three calibrated endodontists (Examiner 1, 2, and 3) will evaluate the radiographs, blinded to the treatment used. Reviewers will assess the radiographs in a dark room using the same imaging software and taking standardized breaks. Preoperative and follow up CBCT will be assessed as described above using PENN 3D criteria. Cases with disagreement will be discussed until joint agreement is reached. Results will be recorded on an excel based score sheet and forwarded to the PI. After all radiographs are jointly agreed on by the examiners, without the interference of the PI, the PI will use the final score sheet(s) and rejoin the information obtained from the calibrated radiograph examination with the data from the material randomization table and information on possible clinical symptoms.

Statistical Analysis:

For subjects returning for 1 year follow up, the following statistical tests are completed:

- 1) Fisher's exact test to evaluate significant association between different healing categories and prognostic factors.
- 2) Logistic regression models were performed to assess odds of complete healing as a linear combination of prognostic factors.

The osteotomy site was considered as the unit of analysis. A probability of $P < .05$ was assigned as the level of significance.

Multiple imputation analysis was performed for cases lost to follow up using SAS statistical software to evaluate the association between the treatment arm and a particular outcome variable (2D healing, 3D healing, 2D outcome and 3D outcome). Under missing at random assumption (MAR), logistic regression analysis using all the variables from the completed cases was used to impute the missing data. Chi-square test for the independence between the outcome variable and treatment variable is carried out for each imputed data and results are pooled to generate a single p-value.

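### Lesion class is listed as prognostic, but no stratification by class is described for single-rooted teeth and no class-adjusted Foundation-versus-control comparison is stated

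*Combined protocol and SAP*

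**What the plan says.** **Eligibility (Protocol, opening paragraph).** "The study includes lesions classes B and C". The two differ in lesion size: "Teeth designated as Class B present with a small periapical lesion", whereas "Teeth with Class C designation have a sizeable periapical lesion with a coronal extension of the lesion".

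**Allocation (Protocol, randomization of the case).** A randomization application is used and "single-rooted teeth will be assigned as either control or test group receiving Foundation". No ratio, block, stratum or minimisation factor is given. Multirooted teeth are split within the tooth: "For multirooted teeth, the mesial root will be randomized, and the distal root will receive the other treatment".

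**Prognostic factors (Protocol, same paragraph).** "Several prognostic factors are evaluated such as subject's sex, age, tooth involved, diagnosis, clinical symptoms, lesion classification". Lesion size on the pre-operative CBCT is listed as a further possible factor.

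**Analysis (Statistical Analysis).** Item 1 is Fisher's exact test of healing categories against prognostic factors. Item 2 is logistic regression of complete healing on prognostic factors. For cases lost to follow-up there is multiple imputation, after which "Chi-square test for the independence between the outcome variable and treatment variable is carried out for each imputed data" and the results are pooled. The unit of analysis is the osteotomy site.

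**The concern.** The plan treats lesion class as something that may affect healing, and class can be known before the draw: examination and CBCT take place at consultation, and randomization follows curettage on the day of surgery. Yet for single-rooted teeth no use of class in allocation is described, and no analysis that names treatment is said to adjust for it. If one arm happens to receive more Class C teeth, and Class C heals differently, part of the raw difference between arms reflects class and not Foundation. A comparison without covariates cannot separate the two.

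At stake are the accuracy of the result given the imbalance that actually occurs, and some precision. Split multirooted teeth are not affected, because both arms receive a site from the same tooth and tooth-level class is balanced by construction.

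**Working it through.** The plan states no sample size, power, class mix or healing rate, so there is no figure of its own to reproduce. Step 1 uses the documents alone; the later steps rest on assumed values.

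**Step 1. Which analysis contains treatment, and which contains class?**

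| Analysis | Treatment named? | Class included? |
|---|---|---|
| Fisher's exact test | No | Yes, as a single factor |
| Logistic regression | No | Yes, it is on the factor list |
| Imputation model | Not by name; uses all variables | Yes, but only to fill in missing outcomes |
| Pooled chi-square | Yes | No |

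No row is stated to hold both in a comparison of the arms. The treatment test for complete cases is not spelled out.

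**Step 2. Chance imbalance in Class C share among single-rooted teeth (assumed: 1:1 allocation, 30% or 50% Class C).**

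With equal arms of n = N/2 and K Class C teeth in all, the number x in the test arm is hypergeometric, and the imbalance is |x/n − (K − x)/n|.

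| N | P(20 points or more), 30% C | P(20 points or more), 50% C |
|---|---|---|
| 20 | 0.63 | 0.66 |
| 40 | 0.30 | 0.34 |
| 60 | 0.16 | 0.20 |
| 100 | 0.05 | 0.07 |

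With unrestricted assignment, the chance of 15 points or more is 0.43, 0.25 and 0.13 for 40, 60 and 100 teeth at 50% Class C, and 0.32, 0.22 and 0.11 at 30%.

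**Step 3. Shift in the raw difference with no treatment effect.**

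Shift = imbalance × healing gap between classes (gap assumed 15 to 30 points).
- 15-point imbalance: 0.15 × 0.15 = 2.25 points; 0.15 × 0.30 = 4.5 points.
- 20-point imbalance: 0.20 × 0.15 = 3 points; 0.20 × 0.30 = 6 points.

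**Step 4. Dilution by split teeth.**

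With n single-rooted sites per arm and M split teeth (one site each per arm), the shift is multiplied by n/(n + M). If M = n, it halves: 6 points becomes 3.

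**Step 5. Effect on type I error.**

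Simulation with no treatment effect: 200,000 replicates per scenario, single-rooted teeth only, equal arms, half Class C, two-sided 0.05. CMH is the Cochran-Mantel-Haenszel test stratified by class.

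| N | Healing B / C | Chi-square, all draws | Chi-square, imbalance of 20 points or more | CMH, same draws |
|---|---|---|---|---|
| 40 | 90% / 80% | 4.9% | 5.2% | 4.4% |
| 40 | 90% / 70% | 5.0% | 5.9% | 4.6% |
| 40 | 90% / 60% | 5.1% | 7.1% | 4.9% |
| 60 | 90% / 80% | 5.3% | 5.9% | 4.6% |
| 60 | 90% / 70% | 4.9% | 6.5% | 4.9% |
| 60 | 90% / 60% | 5.0% | 8.4% | 5.1% |
| 100 | 90% / 80% | 5.5% | 6.3% | 4.9% |
| 100 | 90% / 70% | 5.3% | 8.2% | 5.1% |
| 100 | 90% / 60% | 5.1% | 11.2% | 5.2% |

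Over all draws the unadjusted test holds its level. Given a large imbalance it does not, while the stratified test stays between 4.4% and 5.2%. The worst figure, 11.2%, belongs to N = 100, where such an imbalance has a probability of only 0.07. At N = 40, where the probability is 0.34, the conditional error is 5.2% to 7.1%.

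**The case against.** - **Randomization already deals with this.** Simple randomization is valid, and chance imbalance is part of the sampling error that the test allows for. This stands: a reader might infer that the treatment comparison is biased, and the last table shows that on average it is not. What remains is error given the imbalance that occurs, and lost precision.
- **A model containing class is planned.** A reader might infer that class is ignored throughout the analysis. The documents do not support that, because the logistic regression draws on a list that includes lesion classification. But treatment is not on that list and no sentence makes it a term. Adjustment is therefore unspecified, neither excluded nor promised.
- **The chi-square belongs to the imputation analysis.** True. It should not be read as the whole treatment analysis. The gap on the complete-case side is that no treatment test is stated there.
- **Silence is not evidence.** The text does not show that class was ignored in allocation, only that no use of it is described.
- **The shift is small against noise.** With 80% healing assumed, the standard error of the raw difference is √(2 × 0.8 × 0.2 / n): 12.6, 10.3 and 8.0 points for n = 20, 30 and 50 per arm. A shift of 2 to 6 points is below one standard error in each case. This stands and limits the weight of the point.
- **No evidence that Class C heals worse.** Also true. The documents list class as a factor to evaluate and give no healing rate by class. Nor do they state a class-specific objective, so results by class should be descriptive.

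**Conclusion.** The point holds as a gap in specification. No stratification by class is described for single-rooted teeth, the only test naming treatment is unadjusted, and the plan does not say that its logistic model contains treatment alongside class. A material chance imbalance is plausible if single-rooted teeth are few: about 0.30 to 0.34 for 20 points or more with 40 teeth, and 0.05 to 0.07 with 100. An imbalance of 15 to 20 points shifts the raw difference by about 2 to 6 points, less after pooling with split teeth.

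These sizes depend on assumed numbers of teeth, class mix, 1:1 allocation and healing gap, none of which the documents give. The effect is modest, and the case for acting is that the remedy is nearly free. The conclusion does not extend to split multirooted teeth and does not make the unadjusted test invalid.

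**What to change.** In the Statistical Analysis section, state one class-adjusted treatment comparison and use it for both the complete cases and each imputed data set, in place of the plain chi-square. Suggested wording:

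> *The effect of Foundation on complete healing at 12 months will be estimated by logistic regression with treatment and lesion class (B or C, recorded pre-operatively) as terms, allowing for the pairing of sites within a multirooted tooth. The same model will be fitted to the complete cases and to each imputed data set, with estimates pooled across imputations. Results will also be shown descriptively by class.*

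A Mantel-Haenszel test stratified by class is an acceptable alternative. Treating each split tooth as its own stratum would respect the pairing. For an outcome kept in four healing categories, the generalised form of that test serves the same purpose.

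If allocation is still open, randomizing single-rooted teeth within class, in blocks of varying size, is an optional addition. It needs class recorded before the draw and two lists instead of one. Parts of the Statistical Analysis section are in the past tense, so allocation may be complete; the analysis change is then sufficient on its own.

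The cost is one extra model term and slightly more analysis work. No patients, visits or readings are added, because class is already collected.

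### No rule scores a site extracted or re-operated for endodontic failure before month 12 as failed, so a known failure can be dropped, imputed as healed, or read from an image of the second surgery

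*Combined protocol and SAP*

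**What the plan says.** The Statistical Analysis section introduces the Fisher and logistic tests with "For subjects returning for 1 year follow up, the following statistical tests are completed". The regression is described this way: "Logistic regression models were performed to assess odds of complete healing as a linear combination of prognostic factors". Losses are handled separately: "Multiple imputation analysis was performed for cases lost to follow up using SAS statistical software". The purpose of that analysis is "to evaluate the association between the treatment arm and a particular outcome variable", the outcome variables being 2D healing, 3D healing, 2D outcome and 3D outcome. The imputation model reads: "Under missing at random assumption (MAR), logistic regression analysis using all the variables from the completed cases was used to impute the missing data". Neither loss to follow-up nor the two *outcome* variables are defined, and the unit of analysis is the osteotomy site.

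The Protocol section makes both healing scales image readings: Molven's criteria on periapical films and the modified PENN criteria on CBCT. The worst CBCT category is itself an image finding: "in unsatisfactory healing, the area of low density appears enlarged or unchanged". Periapical films are taken at 6 months. CBCT follows only at one year: "At 12-month follow-up, digital periapical radiographs and CBCT are obtained". Clinical findings are collected throughout: "In all follow-up visits, clinical signs and symptoms are evaluated".

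The only text on extraction concerns a root fracture found during surgery, before randomization. Nothing covers extraction or re-operation during follow-up.

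**The concern.** A site extracted or re-operated because the endodontic treatment failed has a known result: it did not heal. Nothing in the plan records that result.

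- **Extracted site.** It has no 12-month image, and the 3D scale has no earlier follow-up reading. It drops out of the Fisher and logistic tests or, if counted as lost, has its outcome drawn from a model fitted to completed cases. Those cases contain no extraction before the reading, so the model cannot learn that extraction means failure. MAR is hard to defend here, because the reading is missing as a result of the outcome.
- **Re-operated site.** If the patient returns, the month-12 image shows the second surgery, and the site may be scored on that.

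Three results are at stake: the healing rates, the odds ratios for prognostic factors, and the imputed treatment comparison. Without a written rule, the handling may also be settled after the PI has rejoined readings with treatment.

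**Working it through.** The documents give no sample size, healing rate, event rate or dropout figure, so there is no stated figure to reproduce. **Every rate below is assumed.**

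**1. Healing rate.** Let h be the healed share among scored sites and f the share of sites that fail early and go unscored. The true rate is h(1 − f), so the overstatement is h − h(1 − f) = h × f.
- h = 0.75, f = 0.05: 3.75 points.
- Range: 0.60 × 0.01 = 0.6 points to 0.90 × 0.10 = 9.0 points.

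**2. Prognostic-factor odds ratio among returners.** With true healing p and early failure e, the rate among scored sites is p/(1 − e). Take p = 60% vs 80% by a factor; the true OR is 1.5/4 = 0.375.
- e = 8%/2%: 0.60/0.92 = 0.652 and 0.80/0.98 = 0.816; OR = 1.875/4.444 = 0.42.
- e = 5%/5%: 0.632 and 0.842; OR = 1.714/5.333 = 0.32.

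The shift can go either way.

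**3. Imputed treatment comparison, single-rooted teeth.** Take true healing of 60% control and 70% Foundation, a difference of 10.0 points. If the imputation variables reveal a share r of the early failures, the imputed rate is p + e(1 − r)p/(1 − e).

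| Early failure, control/Foundation | r | Control | Foundation | Difference (points) |
|---|---|---|---|---|
| 1%/1% | 0 | 0.606 | 0.707 | 10.1 |
| 5%/5% | 0 | 0.632 | 0.737 | 10.5 |
| 4%/2% | 0 | 0.625 | 0.714 | 8.9 |
| 8%/2% | 0 | 0.652 | 0.714 | 6.2 |
| 2%/8% | 0 | 0.612 | 0.761 | 14.9 |
| 8%/2% | 0.5 | 0.626 | 0.707 | 8.1 |
| 2%/8% | 0.5 | 0.606 | 0.730 | 12.4 |

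At r = 1 the difference is 10.0 in every row.

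**4. Multirooted teeth.** Extraction removes one control and one test site together. The model is bivariate normal latent healing for the two roots, 60%/70% healing and 8%/2% early failure, with the tooth lost if either root fails early. Unfixed: both roots are imputed at the completed-pair rate of their arm. Fixed: the failing root is scored as not healed, and its partner is imputed using that result.

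| Root correlation | Unfixed difference | Fixed difference | Truth |
|---|---|---|---|
| 0.3 | 7.4 | 10.7 | 10.0 |
| 0.5 | 8.5 | 11.4 | 10.0 |
| 0.6 | 9.0 | 11.7 | 10.0 |

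At correlation 0.3 the arm rates are 0.656 and 0.731 unfixed, against 0.602 and 0.709 fixed (truth 0.600 and 0.700). The fix brings both arm rates closer to the truth at all three correlations. It improves the difference only below a correlation of about 0.5.

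**5. Significance.** A grid took 30 or 50 sites per arm, 80% or 90% success among readable sites, and 0 to 5 early failures in control against 0 or 1 in test. The most unequal case (30 per arm, 90%, 5 vs 0) goes from 22/25 = 88.0% vs 27/30 = 90.0% (Fisher p = 1.00) to 22/30 = 73.3% vs 90.0% (p = 0.18). No scenario crosses 0.05.

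**The case against.** The strongest reply is that the plan is silent rather than wrong. Much of that stands.

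- **A reader might infer that the plan excludes every such site from the 1-year tests.** It does not say so. The restriction is by subject, so a patient who attends at month 12 after re-operation stays in. That site's problem is a misleading image, not exclusion.
- **A reader might infer that such a site never has a follow-up reading.** That is true for 3D only. A 6-month film can already give a 2D category, including unsatisfactory. What is missing is a rule that carries it into the 1-year result.
- **The undefined 2D and 3D outcome variables, or the joining of readings with symptoms, might contain a failure rule.** None is written, so they do not close the gap.
- **Imputation uses all variables, and symptoms are recorded at each visit.** The error does shrink as far as these reveal the failure (r in the working).
- **Impact is assumed throughout.** This is correct. With equal failures by arm the treatment difference barely moves, and the large shifts need a fourfold imbalance.
- **Scoring a site unsatisfactory without an image departs from the CBCT definition.** It does, and the departure should be stated openly. The alternative is to treat a known failure as unknown.

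A failing site still in place and not re-operated at month 12 is unaffected, because it can be read as unsatisfactory.

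**Conclusion.** The concern holds as a gap with a predictable direction for healing rates. No written rule scores these sites as failed, and the rules that are written lead to omission, imputation from completed cases, or a reading of the second surgery.

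If such events occur and are handled this way, healing is overstated by about h × f: 3.75 points at h = 0.75 and f = 0.05, with an assumed range of 0.6 to 9.0. Prognostic odds ratios can move either way. The treatment difference is biased mainly when early failures differ by arm.

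A reader might go further and infer that reported healing is certainly inflated or that the treatment conclusion would change. The documents support neither: they give no event rate, the effect may be small, and no scenario checked crossed the 0.05 level. The change is worth making because it is cheap and the outcome of these sites is known. Confidence is medium.

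**What to change.** In the Statistical Analysis section:

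1. Score as not healed, in the 2D and 3D analyses, each randomized site extracted or re-operated for endodontic failure of its own root before the 12-month reading, whatever a later image shows. Include these sites in the Fisher, logistic and treatment-arm analyses.
2. Assign the cause from the chart before treatment is rejoined with the readings.
3. Define loss to follow-up so that it excludes these sites. Impute only sites of unknown status: non-returners, teeth lost for other causes, unaffected partner roots, and roots where it is unclear which one failed. Use the 6-month reading, follow-up symptoms and the partner root's result as predictors.
4. Add one worst-case, non-MAR sensitivity analysis of the imputed sites. With an unknown share u per arm and an observed difference d, its range is (1 − u)d ± u. At d = 10 points this gives 4.5 to 14.5 for u = 5%, and −1 to 19 for u = 10%.

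The cost is SAP wording and a small chart review, with no new visits or images. Reported healing rates will be slightly lower. Partner-root bias remains in multirooted teeth: the fix improves the arm-level rates, but the multirooted difference improves only when root correlation is below about 0.5. That limit should be reported with the result.

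### Fisher's exact test is planned for four numeric prognostic factors with no cut-off given: any grouping costs power, and nothing rules out a cut chosen on outcome

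*Combined protocol and SAP*

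**What the plan says.** The Protocol section names the prognostic factors. The general list includes "sex, age, tooth involved, diagnosis, clinical symptoms, lesion classification". The list of preoperative CBCT factors adds three measured quantities:

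- "Thickness of the buccal bone: measured 3 mm coronally from the apex on the B-L view"
- lesion size, for which "The value of the largest dimension was recorded as the lesion size"
- "Root angulation: measured between the long axis of the root and a line tangent to the cortical plate at the resection area"

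Age and these three are numbers. The remaining factors (sex, tooth, diagnosis, clinical symptoms, lesion class, cortical fenestration, previous treatment) are categories.

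The Statistical Analysis section lists two analyses for subjects seen at one year. Item 1 is "Fisher's exact test to evaluate significant association between different healing categories and prognostic factors", with no restriction to categorical factors. Item 2 reads "Logistic regression models were performed to assess odds of complete healing as a linear combination of prognostic factors" and does not say how numeric factors are coded. "The osteotomy site was considered as the unit of analysis", and "A probability of $P < .05$ was assigned as the level of significance". No cut-off, grouping or rule for choosing one appears anywhere, and no sample size, expected healing rate or effect size is stated.

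**The concern.** Fisher's exact test works on a cross-table of groups. To apply item 1 to a thickness, a length, an angle or an age, someone must first divide the values, and the plan does not say where. Two costs can follow.

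- **Lost power.** This follows from grouping as such, even at a neutral point such as the median. A real association between a CBCT measurement and healing is then easier to miss.
- **False positives.** This arises only if the cut is chosen because of how it relates to healing. The plan leaves room for it. There are two healing scales (periapical and CBCT) with four grades each, several possible cuts per marker, and a significance level for which no multiplicity adjustment is described.

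At stake is the prognostic-factor question, which both items listed for one-year returners address: a useful marker overlooked, or a threshold reported that is not real.

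**Working it through.** The plan gives no figure of its own to reproduce, so the check sets the costs of grouping against an uncut analysis over assumed ranges.

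**Inputs from the document.** Fisher's exact test (Statistical Analysis, item 1); four numeric factors (Protocol section); level 0.05, taken as two-sided; osteotomy site as unit.

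**Assumed inputs.** 60 or 100 independent sites; complete healing in 60 to 75%; a normally distributed marker, with logit P(complete healing) = a + b × marker in SD units. Slopes b = 0, 0.6 and 0.8 correspond to odds ratios per SD of 1, exp(0.6) = 1.82 and exp(0.8) = 2.23.

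**Step 1: information lost at the median.** For a normal marker a median split retains about 2/π = 0.64 of the information, so about 36% is lost.

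**Step 2: simulation.** With 1,500 simulated trials per setting, the percentage with P < .05 ranged as follows over the assumed settings:

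| Analysis | No effect | OR 1.82 per SD | OR 2.23 per SD |
|---|---|---|---|
| Fisher, fixed median split | 2.6–3.7 | 23–54 | 39–76 |
| Rank test, uncut values | 4.2–6.1 | 46–79 | 67–94 |
| Fisher, best of three quartile cuts | 7.5–9.5 | – | – |
| Fisher, best of 13 cuts (20th to 80th percentile) | 17.5–18.7 | – | – |

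Comparing the ends of the ranges, the power difference is 46 − 23 = 23 and 79 − 54 = 25 points at OR 1.82, and 67 − 39 = 28 and 94 − 76 = 18 points at OR 2.23. That is roughly 20 to 30 points, narrowing where the rank test nears its ceiling. Repeated runs of the same design put the best-of-13 false-positive rate between 16 and 21%.

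**Step 3: how much of the gap is due to cutting?** A Pearson test at the same median cut separates the effect of cutting from Fisher's conservatism. At OR 1.8, 70% healed and 60 sites, power was 26% (Fisher), 33% (Pearson) and 46% (rank). The total gap is 46 − 26 = 20 points, of which 33 − 26 = 7, or 7/20 = 35%, comes from Fisher's test and the other 13 from the cut. Over all settings Pearson recovered 7 to 11 points of a 19 to 28 point gap.

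**Step 4: wider assumptions.** A second simulation (4,000 trials per setting; 50 to 160 sites; healing 50, 70 or 85%; OR 1.75 or 2.0 per SD) compared the median-split Fisher test with a logistic likelihood-ratio test on the continuous marker.

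- The gap ran from 98.7 − 88.2 = 10.5 points (160 sites, 50% healed, OR 2.0) to 57.2 − 26.3 = 30.9 points (50 sites, 70% healed, OR 2.0).
- With no effect, the fixed median split rejected in 2.2 to 3.9% of trials and the continuous test in 4.8 to 6.1%.
- Searching every cut from the 10th to the 90th percentile rejected in 23 to 38%.

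**The case against.** The strongest reply is that item 2 already does what is asked. A model that is linear in the prognostic factors would ordinarily take numeric factors as they are, and its outcome, complete healing, is the one simulated here. That is a fair reading and it softens the point. It does not remove it: the coding is not stated, the same grouped variables could be used in both items, and the item 1 P-values would still be reported.

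A reader might infer that the cuts will be picked after outcomes are known. The document does not say so. The CBCT factors are measured before surgery, about a year before the 12-month outcome, so groups could be fixed early. The sentence on rejoining data concerns examiner scores, the randomisation table and symptoms, not cut-offs. A reader might also infer that the planned test inflates false positives as it stands. At a pre-fixed cut it does not; it is conservative. Nor does a median split discard most of the information: the loss is about 36%.

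The number of sites, healing rate and effect sizes are assumptions, and the simulations used a binary outcome and independent sites. Item 1 has several healing categories, and a multirooted tooth can give two sites that share one age. The exact percentages therefore should not be leaned on. The power loss did appear in every setting tried.

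**Conclusion.** The concern holds in limited form. Item 1 applies a test for categories to four numeric factors without saying how they become categories.

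- Under the assumed 60 to 100 sites and 60 to 75% healing, a median split with Fisher's test costs roughly 20 to 30 points of power at odds ratios of 1.8 to 2.2 per SD, about a third of it from Fisher's conservatism in the worked case.
- False positives stay at about 2 to 4% with a cut fixed in advance. They would reach about 16 to 21% per marker only if someone searched 13 cuts for the best P-value, which the plan neither describes nor excludes.

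The point concerns the prognostic-factor analysis. It gives no reason to doubt the randomised comparison of filled and unfilled sites. It is worth correcting because a better analysis of the same data is available at almost no cost.

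**What to change.** In the Statistical Analysis section:

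1. Restrict Fisher's exact test in item 1 to sex, tooth, diagnosis, clinical symptoms, lesion class, fenestration and previous treatment.
2. Test age, buccal bone thickness, lesion size and root angulation uncut, with a Wilcoxon rank-sum test for complete versus not complete healing.
3. State that these four enter the item 2 logistic model as continuous terms, with odds ratios per mm, per degree and per 10 years.
4. Allow for two sites in the same tooth, for example with standard errors clustered by tooth in the logistic model. The plain rank-sum test also treats sites as independent, so the plan should say how it handles such pairs.
5. Label any grouping of these factors as descriptive.

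This takes a few sentences and no new data. The price is a less simple presentation than a high/low table, which can still be shown descriptively. The change does not deal with multiplicity: four independent markers each tested at 0.05 still give 1 − 0.95⁴ = 18.5% for at least one false positive, so the results should be reported as exploratory or adjusted.
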